4.2.2 Number of centres participating

This protocol is a multicentric study with 27 tertiary nephrology centres anticipated to participate.

4.2.3 Identification of the subjects

For this research, the subjects will be identified as follows: Centre No. (3 numerical positions) - Selection order No. of the person in the centre (4 numerical positions) - surname initial - first name initial

This reference is unique and will be retained for the entire research period.

4.2.4 Randomization

Randomization will be stratified according to centre and will use permutation blocks, the size of each being not available to clinicians.

Centralised randomization will be carried out by the investigator after inclusion using the cleanWeb system (Telemedecine).

5 PROCEDURE FOR THE RESEARCH

5.1 Inclusion visit

This inclusion visit takes place after at least 15 +/- 2 days of RAS blocker treatment (low dosage if eGFR < 45 ml/min/1,73m², and median dosage if eGFR \ge 45 ml/min/1,73m², equivalence tables being provided, see 16.3).

Clinical examination will be performed with sitting blood pressure measurement, checking for postural hypotension, weight measurement, general and cardiovascular examination. Urin and blood parameter should be available (≤ 7 days before inclusion visit): blood counts, plasma sodium, potassium, total proteins, urea, serum creatinine (enzymatic IDMS-traceable assay).

Inclusion and exclusion criteria, including histologic and clinico-biologic criteria, will be checked. The study will be presented and proposed by the nephrologist to the patient and the inform consent will be signed. The investigator will then complete an electronic enrolment form, accessible 24/7 on the internet via the e-CRF (secured access will be obtained in advance by each pre-declared investigator centre). Randomization will be carried out by a system of random allocation linked to the electronic case report form, in such a way that a patient enrolled in the form will be easily and automatically randomized.

For the control group, a one-day hospitalization for first mGFR (if available) will be organised according to local practices, as soon as possible within 21 days after the randomisation.

For the experimental group, 3 successive one-day hospitalizations for initation of therapy with methylprednisolone pulses (one per day) and first mGFR (if available) will be scheduled according to local practices, as soon as possible within 21 days after the randomisation. These 3 pulses will be followed at D3 morning by oral corticosteroids during 4 months. First mGFR will be performed before the first methylprednisolone pulse.

The one-day hospitalization (for the control group if mGFR is available), or the date of randomisation (for the control group if mGFR is not available), or the first day of the 3 oneday hospitalizations (for the experimental group) will be considered as D0 in this study, to organize follow-up visits.

If the patient is not hospitalized at D0 (control group and mGFR not available), the biological collection will be performed during the inclusion visit: DNA, blood and urine.

If the patient is hospitalized at D0, will be performed during the first day of hospitalization:

- Medical interview evaluating compliance for treatments and lifestyle recommendations

- Clinical examination with sitting blood pressure measurement, checking for postural hypotension, weight measurement, general and cardiovascular examination, and ethnic origin (caucasian, asiatic, african, african-american). The ethnic origin is necessary to calculate eGFR by the CKD-EPI formula.

eGFR =141 x min(SCr/ κ , 1) α x max(SCr / κ , 1)-1.209 x 0.993Age x 1.018 [if female] (or x 1.159 [if Black])

Abbreviations/units

eGFR (estimated glomerular filtration rate) = mL/min/1.73 m²

$$\begin{split} S_{Cr} & (standardized \ serum \ creatinine) = mg/dL \\ \kappa &= 0.7 \ (females) \ or \ 0.9 \ (males) \\ \alpha &= -0.329 \ (females) \ or \ -0.411 \ (males) \\ min &= indicates \ the \ minimum \ of \ S_{Cr}/\kappa \ or \ 1 \\ max &= indicates \ the \ maximum \ of \ S_{Cr}/\kappa \ or \ 1 \\ age &= years \end{split}$$

- Biochemistry: plasma sodium, potassium, albumin, total proteins, bicarbonate, chlorure, fasting glycemia, total and LDL cholesterol, triglycerides, urea, uric acid, serum creatinine (enzymatic IDMS-traceable assay), C reactive protein. Urinary protein, creatinine, sodium and urea will be evaluated on a 24-hour urinary collection (or urinary sample).

- Haematology: blood count.

Biochemistry and haematology analyses are associated with care.

- Biological collection : DNA, blood and urine (for the experimental group, before the first methylprednisolone pulse.

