6.2 Exclusion criteria

- a. >30% increase of serum creatinine within 15 days after starting RAS blockade therapy
- b. >50% cellular/fibrocellular crescents, or >50% tubulointerstitial fibrosis or >50% globally sclerotic glomeruli
- c. >50% plasma creatinine increase within the last 3 months before the renal biopsy
- d. Nephrotic syndrome with minimal change disease and IgA deposits
- e. eGFR <20 ml/min/1,73m² (CKD-EPI formula) within 30 days before or after the renal biopsy
- f. Uncontrolled blood pressure (Systolic blood pressure >180 mmHg or diastolic blood pressure > 110 mmHg)
- g. Previous corticosteroids treatment (>20 mg/d during more than 15 days, within the last 3 months before the renal biopsy)
- h. Pregnancy or breast feeding or women without sufficient contraception
- i. Secondary known forms of IgAN
- j. Henoch-Schoenlein purpura
- k. Additional other chronic renal disease
- Contraindication for immunosuppressive therapy, including active intestinal bleeding, active gastric or duodenal ulcer; active infection; any malignancy in a last years before the inclusion; severe psychiatric disease; living vaccines; anti-inflammatory dosages of acetylsalicylic acid
- m. Contraindication for RAS blockade therapy
- n. Known allergy or intolerance to corticoids or lactose

o. Organ transplant patient

The absence of measured GFR availability on the site is not an exclusion criterion.

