7.2.2 Non-experimental medication used in all patients

The following treatments are part of current recommendations for IgAN treatment.

Vitamin D supplementation is recommended for all patients according to the patient physician discretion, with a minimum vitamin D administration equivalent to colecalciferol: 100000 UI each 3 months.

Dietary regimen and lifestyle counseling is provided during consultations or hospitalization, with the following objectives:

- Avoiding high protein intake (>1,3 g/kg/d)
- Lowering salt intake to <90 mmol/d of sodium (corresponding to 5 g of sodium chloride)
- Undertaking physical activity compatible with cardiovascular health and tolerance
- Achieving a healthy weight (BMI 20 to 25)
- Stop smoking.

Treatment with RAS blockade therapy (one molecule or in association) is systematically administred in all patients.

RAS blockade with ACE-inhibitors or angiotensin receptor blockers is initiated using the drug chosen by the patient physician. Low dosage is initiated if eGFR is <45 ml/min/1,73m².

Medium dosage is initially used if eGFR is >45 ml/min/1,73m². Every modification of RAS blockade is followed by a control of plasma creatinine and potassium within 3 weeks. These results can lead to diminution or interruption of RAS blockade according to local decision. RAS blockade should be increased at each visit to achieve the following objectives, according to the patient physician decision:

- Blood pressure <130/80 mmHg while sitting
- PCR <0,5 g/g or PCR <0.75 g/g and <30% of initial PCR

Patients can be converted to an ARB when an ACE-inhibitor is not tolerated. Dose equivalence tables for ACE-inhibitors and ARB's will be provided. Bitherapy with ACE inhibitors and ARB is allowed. All other antihypertensive medications, including diuretics, calcium-channel blockers and ß-blocker can be used at any time-point during the study depending on the clinical decision of the patient physician.

Hyperkalemia is treated according to current guidelines.

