9 STATISTICAL ASPECTS

9.1 Calculation of sample size

Given the results of previous studies, we assume that 60% of the patients in the control group will achieve the failure criteria at 24 months. We aim to obtain a decrease to 35% of failure with early corticotherapy (i.e in the experimental group). With 80% power and an 2-sided alpha risk equal to 5%, 61 subjects per group are required. Consequently, 122 patients will be included in this study.

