13 ETHICAL AND LEGAL CONSIDERATIONS

13.1 Methods for obtaining information and consent from research participants

In accordance with Article L1122-1-1 of the French Public Health Code, no biomedical research can be carried out on a person without free and informed consent, obtained in writing after the person has been given the information specified in Article L.1122-1 of said Code.

The subject will be granted a reflection period of 15 days between the time when the subject receives the first information (during the screening phase) and the time when he or she signs the consent form.

The free and informed consent, in writing, of the subject is obtained by the investigator, or by a doctor representing the investigator, before the inclusion of the subject in the research.

The information sheet and a copy of the consent form, signed and dated by the research subject and by the investigator or the doctor representing the investigator, are given to the individual prior to his or her participation in the research.

In addition, the investigator will specify in the research participant's medical file the methods used for obtaining his or her consent as well as the methods used for providing information

with the goal of obtaining their consent. The investigator will retain the original signed and dated copy of the subject's consent form.

The patient is considered as include in the research at the moment of his(her) randomization.

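### Protocol section 5.1 lets the 15-day RAS tolerance exclusion (6.2a) be cleared on a creatinine from day 6 or day 8 of RAS blockade

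*Protocol*

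**What the plan says.** Protocol section 5.1 fixes the timing of the inclusion visit: "This inclusion visit takes place after at least 15 +/- 2 days of RAS blocker treatment". On laboratory results it says: "Urin and blood parameter should be available (≤ 7 days before inclusion visit"; serum creatinine is on that list. At the same visit, "Inclusion and exclusion criteria, including histologic and clinico-biologic criteria, will be checked", consent is signed and the patient is randomised. Section 13.1 confirms that this is the point of entry: "The patient is considered as include in the research at the moment of his(her) randomization".

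Exclusion a in section 6.2 reads: ">30% increase of serum creatinine within 15 days after starting RAS blockade therapy". Neither section names the creatinine from which the 30% rise is measured.

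The only other rule on creatinine after a RAS change is in section 7.2.2: "Every modification of RAS blockade is followed by a control of plasma creatinine and potassium within 3 weeks". The chronology table in section 5.4 marks biochemistry from D0 onwards and none at inclusion.

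**The concern.** The exclusion has a 15-day horizon, but the visit at which it is checked can fall before that horizon ends, and the creatinine can be older still. A rise above 30% that appears after the sample and by day 15 would be found only after randomisation. Both arms are built on RAS blockade, and this is the only creatinine-based test of RAS tolerance before entry, so the protocol's own exclusion would not be fully applied.

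There is also a possible effect on the endpoint. If a late RAS-related rise in creatinine follows the baseline GFR and persists, it can be counted as GFR loss although it says nothing about steroids.

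**Working it through.** **Inputs.** All are from the Protocol. Section 5.1: visit at 15 days with a tolerance of 2, laboratory age 0 to 7 days, D0 up to 21 days after randomisation, CKD-EPI exponent −1.209 for creatinine above κ. Section 6.2a: rise above 30% within 15 days. Sections 4.1.1 and 4.1.2: GFR below 80% of initial.

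**Day of the creatinine.** RAS day of sample = visit day − age of result. Unobserved days = 15 − RAS day of sample, or 0 if negative.

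| Visit day | Age of result | RAS day of sample | Unobserved days to day 15 |
|---|---|---|---|
| 13 | 7 | 13 − 7 = 6 | 15 − 6 = 9 |
| 13 | 0 | 13 | 2 |
| 15 | 7 | 15 − 7 = 8 | 15 − 8 = 7 |
| 15 | 0 | 15 | 0 |
| 17 | 7 | 17 − 7 = 10 | 15 − 10 = 5 |
| 17 | 0 | 17 | 0 |

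Dropping the tolerance alone does not close the gap, because the day-15 visit still admits a day-8 sample. With results up to 7 days old, a sample from day 15 or later is guaranteed only for visits from day 15 + 7 = 22.

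**Does another rule close the gap?** The control in section 7.2.2 has a limit of 3 weeks, so it may come after randomisation. The D0 biochemistry falls on or after the randomisation date, so it is not the eligibility check.

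**Size of a missed rise on the eGFR scale** (creatinine above κ, other terms unchanged):
- A 30% rise gives 1.3^(−1.209) = 0.728 of the earlier eGFR, a fall of 27%.
- The 80% limit is crossed at 0.8^(−1/1.209) = 1.203, a rise of 20.3%.

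A rise large enough for exclusion a would therefore cross the 80% limit, if the initial eGFR precedes it and it persists.

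**Which baseline applies?** Section 4.1 takes GFR at D0. Under section 5.1:
- Experimental patients are hospitalised at D0, with fresh serum creatinine, within 21 days after randomisation.
- Controls with measured GFR are likewise hospitalised at D0 on the same terms.
- Controls at centres without measured GFR have the randomisation date as D0. The full D0 panel is listed for hospitalised patients, so the only creatinine that 5.1 clearly requires for them is the inclusion sample. The table in 5.4 does mark tests at D0, so a same-day sample may be taken; the text does not settle it.

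**Sample size.** Section 9.1 uses 60% against 35% failure, 80% power and two-sided 5%. With pooled variance, n = [1.96·√(2·0.475·0.525) + 0.842·√(0.24 + 0.2275)]² / 0.25² = 61.4 per group, against the stated 61. None of these inputs depends on the inclusion timing.

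**The case against.** The strongest reply is that the baseline is not the inclusion creatinine. For all experimental patients, and for controls with measured GFR, initial GFR is taken at a D0 hospitalisation that may be up to 21 days after randomisation. Where that day is RAS day 15 or later, a rise between day 6 or 8 and day 15 is already in the initial value. This stands, and it confines the endpoint effect to controls at centres without measured GFR and to patients whose D0 falls before RAS day 15.

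A second reply is that a day-6 or day-8 sample does lie within 15 days of starting, and that 5.1 sets a maximum age for a panel without making it the only evidence for exclusion a. That is fair as to wording: a site may draw a later sample. Nothing requires it to.

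Third, section 7.2.2 expects RAS blockade to be raised during follow-up and allows it to be reduced locally, so RAS-related GFR changes after baseline occur whatever the screening. This also stands. It limits what better screening can achieve, but gives no reason to leave a stated exclusion partly unapplied.

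Two stronger readings are tempting. A reader might infer that every patient who slips through becomes a treatment failure. The documents do not support that: D0 often absorbs the rise, and the primary endpoint needs the loss to be present at 24 months. A reader might also infer that such controls would meet the month-2 deterioration rule in section 7.4.1. A 30% rise leaves eGFR at 72.8% of the earlier value, above the 70% limit. Reaching it needs a rise of 34.3% (0.7^(−1/1.209) = 1.343) after the initial value, and the rule calls for a second sample at least 14 days later.

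**Conclusion.** The point holds as a contradiction within section 5.1 and a mismatch with exclusion a. A site can comply and still clear the exclusion on a day-6 creatinine (day 8 without the tolerance), leaving 9 (or 7) of 15 days unobserved before randomisation. Those figures are the edge of what is permitted, combining the earliest visit with the oldest allowed result; a same-day sample at a visit on day 15 or later leaves no gap.

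The established consequence is that some patients whom the protocol means to exclude can be randomised. Misattributed GFR decline is possible only where the baseline precedes the rise. The documents give neither the frequency nor the timing of rises above 30%, so the number affected is unknown. The gap in eligibility applies to both arms alike, and the sample size is untouched. This should be corrected, but it does not threaten the trial's main comparison on the evidence available.

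**What to change.** Reconcile sections 5.1 and 6.2a:
- Remove the conflict between a minimum number of days and a two-sided tolerance around it.
- Tie the creatinine used for exclusion a to the end of the protocol's own 15-day window, and require the result before randomisation.
- Name the pre-RAS creatinine against which the 30% rise is judged.
- Show the inclusion sample in the chronology table in section 5.4.

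How the criterion applies to patients already on RAS blockade for longer is for the sponsor to reconcile. Comparing a current value with one from before a distant RAS start could exclude patients for disease progression instead of RAS intolerance.

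The cost is small: the timing of a sample already required changes. Some inclusion visits or samples would move by a few days, at most 9 (from day 6 to day 15). The 45-day biopsy limit in section 6.1 accommodates this when RAS blockade starts soon after the biopsy.

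### At centres without measured GFR, initial eGFR is taken at randomisation in controls but up to 21 days later in the experimental arm, which can tilt the GFR components of the primary endpoint

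*Protocol*

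**What the plan says.** Section 5.1 gives three definitions of day 0:

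- Control patient, mGFR available: the one-day hospitalisation. "For the control group, a one-day hospitalization for first mGFR (if available) will be organised according to local practices, as soon as possible within 21" (the limit is in days, counted from randomisation).
- Control patient, mGFR not available: "or the date of randomisation (for the control group if mGFR is not available").
- Experimental patient at any centre: "or the first day of the 3 oneday hospitalizations (for the experimental group) will be considered as D0 in this study, to organize follow-up visits". The pulses "will be scheduled according to local practices, as soon as possible within 21 days after the randomisation".

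The footnote to the chart in section 5.4 repeats this: for controls without mGFR, day 0 is the inclusion and randomisation consultation.

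Section 5.1 schedules the day-0 biochemistry for patients who are hospitalised at day 0. At a centre without mGFR that means the experimental arm alone. The inclusion visit has its own requirement: "Urin and blood parameter should be available (≤ 7 days before inclusion visit"), and serum creatinine is on that list.

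Section 4.1 places GFR at day 0, month 12 and month 24, with eGFR where mGFR is unavailable. Section 4.1.1 then counts as failure a GFR below 80% of the initial value, or a loss of more than 10 ml/min/1.73m² from it.

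On background treatment, section 5.1 says "This inclusion visit takes place after at least 15 +/- 2 days of RAS blocker treatment", at a low or median dosage, and section 7.2.2 says "RAS blockade should be increased at each visit to achieve the following objectives, according to the patient physician decision". Section 6.2 states that lack of mGFR at a site is not an exclusion criterion. The number of such sites is not given.

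**The concern.** Both GFR components of the primary endpoint are measured against an initial value. If the rule for that value depends on the arm, the two failure rates are not on the same footing even when treatment does nothing.

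The gap need not be neutral. Patients enter on a starting dose of RAS blockade. If the dose is raised at the inclusion visit, the increase comes after the control baseline and before the experimental one. The protocol expects RAS blockade to affect creatinine: exclusion a in section 6.2 removes only rises above 30%, and section 7.2.2 asks for a creatinine check within 3 weeks of every change, about the length of the gap. A further fall in GFR would lower the experimental baseline only, and so reduce the GFR failures counted in that arm. The experimental baseline is also measured after allocation is known.

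Stratifying randomisation by centre does not help, because the asymmetry arises within a centre. The 6-month failure definition in section 4.1.2 and the rescue criteria in section 7.4.1 also refer to initial eGFR, so a higher control baseline would reach those thresholds more often too.

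**Working it through.** **The plan's sample size.** Section 9.1 assumes 60% versus 35% failure, 80% power and two-sided 5%. With pooled variance, n = [1.96·√(2·0.475·0.525) + 0.842·√(0.60·0.40 + 0.35·0.65)]² / 0.25² ≈ 61.4, so 62 per arm against the stated 61. Power at 61 per arm is 79.7%. The figure reproduces and is not in question.

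**How far apart the baselines can be.** The experimental baseline is up to 21 days after randomisation. The scheduled control creatinine is up to 7 days before the inclusion visit. The maximum gap is 21 + 7 = 28 days.

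**Ordinary disease progression.** Section 2.2 gives declines of 3.1 and about 5 ml/min/1.73m² per year. Decline = rate × days / 365:

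- 21 days: 0.18 to 0.29
- 28 days: 0.24 to 0.38

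Follow-up length barely differs. Section 5.2 counts visits from each patient's own day 0, so from baseline sample to month 24 the control interval is at most 7 days longer, worth 0.06 to 0.10 ml/min/1.73m².

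**A RAS-related fall inside the gap.** The documents give no figure, so a range is assumed. Two million patients were simulated under no treatment effect. The assumptions, none of them from the documents except the two mean slopes, were:

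- baseline GFR mean 60, SD 20, with a floor of 22
- mean slope 3.1 or 5 per year, SD 5
- measurement SD 4
- 30% failing on proteinuria, independently of GFR

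Both GFR thresholds of section 4.1.1 were applied. Composite failure without any shift was about 58% (slope 3.1) or 67% (slope 5), on either side of the plan's 60%. A shift was then added to the control baseline only.

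With failure rates p1 and p2, d = p1 − p2 and 61 per arm, the chance of rejection is Φ((d − 1.96·se0)/se1) + Φ((−d − 1.96·se0)/se1), where se0 is the pooled and se1 the unpooled standard error. Ranges cover the two slopes.

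| Shift (ml/min/1.73m²) | Points added to control failure, all centres without mGFR | Type I error | Points added, half of patients at such centres | Type I error |
|---|---|---|---|---|
| 0.38 | 0.8–0.9 | 5.1% | 0.4 | 5.0% |
| 1 | 2.2–2.3 | 5.7–5.8% | 1.1 | 5.2% |
| 2 | 4.5 | 7.9–8.4% | 2.2–2.3 | 5.7–5.8% |
| 3 | 6.7–6.8 | 11.9–12.8% | 3.4 | 6.7–6.8% |

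Worked example, slope 5, shift 2, all centres: p1 = 0.714, p2 = 0.669, d = 0.045, se0 ≈ se1 ≈ 0.0836. The two terms are about 0.078 and 0.006, giving 8.4%.

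**The case against.** The best reply is that day 0 is only a visit clock. Section 5.1 defines it for organising follow-up, and no section ties initial eGFR to a named sample. The chart in section 5.4 marks biochemistry at day 0 and not at inclusion, so control tests could be read as due on the randomisation day, and the statistical analysis plan may name the sample. This narrows the gap from 28 to 21 days but does not close it. Section 4.1 places GFR at day 0, and day 0 depends on the arm.

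The mechanism is also unproven. The 15 days on RAS blockade are a minimum, so not every patient is newly started. The 15-day period in exclusion a lies mostly before inclusion. No visit is scheduled between inclusion and the experimental day 0, so among scheduled visits only a change at inclusion could act in the gap. The 21 days are a maximum. All of this stands, and it limits the claim to a possible tilt.

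A reader might infer three stronger things that the documents do not support.

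- **Unequal follow-up.** It is in effect equal, because each patient's visits run from that patient's own day 0.
- **A tilt through proteinuria.** The primary criterion is an absolute 0.5 g/g, so initial PCR does not enter it. In the 6- and 12-month definitions a lower initial PCR makes the 30% clause easier to meet, which would work against the experimental arm.
- **About 4 points per 1 ml/min.** With mean loss set exactly at 10 and SD 10, P(loss > 10) = 1 − Φ(shift/10) falls from 50% to 46%, 42% and 38% for shifts of 1, 2 and 3. That covers one component at close to its greatest sensitivity. On the composite the figure is about 2 points.

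The ±1 month window at month 24 is wider than the gap, but it applies to both arms and adds noise. It does not cancel a shift in one direction.

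**Conclusion.** The concern holds as a possible bias with a known direction and an unknown size. At centres without mGFR the protocol as written takes the control baseline at or before randomisation and the experimental baseline up to 21 days after open-label allocation. If GFR falls further under RAS blockade in between, the GFR components favour the experimental arm.

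Ordinary progression alone is negligible. A material effect needs a further RAS-related fall of about 2 ml/min/1.73m² or more and many patients at centres without mGFR. The documents give neither figure, so a reader should not conclude that bias has been shown. Under the assumptions above, a fall of 1 to 3 ml/min/1.73m² adds about 2 to 7 points to control composite failure in the extreme case. With half of patients affected, a fall of 1 to 2 gives a type I error of about 5.2 to 5.8%. It is worth correcting because the remedy costs almost nothing.

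**What to change.** In sections 4.1 and 5.1, and in the analysis plan, state that at centres without mGFR initial eGFR is, in both arms, the value from the pre-randomisation inclusion creatinine. Use it for the GFR components in section 4.1.1 and for the eGFR-based failure definitions in section 4.1.2. Section 7.4.1 uses the same term, so the protocol should say which value is meant there and reconcile the sections. At centres with mGFR keep the day-0 values, since both arms are measured within 21 days after randomisation.

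Keep day 0 as the visit clock. Counting visits from randomisation would separate experimental visits from the steroid course, the month-2 dispensation and the pharmacokinetic samples, for no real gain. Also reconcile section 5.2, which counts month 24 from day 0, with section 5.3, which counts it from the first GFR measurement.

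The cost is wording only: no new visit or sample. One small downside is that the experimental baseline would then lie up to 28 days before the first pulse. Its interval to month 24 would be up to 21 days longer than the control's, worth 0.18 to 0.29 ml/min/1.73m² at the plan's own slopes, or under 1 point of composite failure.
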